**Table 1 Criteria for Temporary Discontinuation of Study Drug, Dose Reduction, and Resumption of Treatment**

Dose Modification Guidelines for Lenvatinib Related Toxicity		
Treatment-Related Toxicitya,b	Management	Dose Adjustment
Grade 1 or Tolerable Grade 2		
	Continue treatment	No change
Intolerable Grade 2c,d or Grade 3e		
First occurrence	Interrupt lenvatinib until resolved to Grade 0-1, or tolerable Grade 2	11.2 mg/m  (or 20% reduction of the starting dose) orally QD (one-level reduction)
Second occurrence (same toxicity or new toxicity)	Interrupt lenvatinib until resolved to Grade 0-1, or tolerable Grade 2	9.0 mg/m  (or 20% reduction of the previous dose) orally QD (one-level reduction)
Third occurrence (same toxicity or new toxicity)	Interrupt lenvatinib until resolved to Grade 0-1, or tolerable Grade 2	7.2 mg/m  (or 20% reduction of the previous dose) orally QD (one-level reduction)
Fourth occurrence (same toxicity or new toxicity)	Interrupt lenvatinib	Discuss with sponsor
Grade 4f: Discontinue Study Treatment		

Note: For grading see [CTCAE version 5.0](#). Collect all CTC grades of adverse events, decreasing and increasing grade.

BMI = body mass index, CTCAE = Common Terminology Criteria for Adverse Events

- a: An interruption of study treatment for more than 28 days will require sponsor's approval before treatment can be resumed.
- b: Initiate optimal medical management for nausea, vomiting, hypertension, hypothyroidism, and/or diarrhea prior to any study treatment interruption or dose reduction.
- c: Applicable only to Grade 2 toxicities judged by the subject and/or physician to be intolerable.
- d: Obese subjects with weight loss do not need to return to the baseline weight or 10% of baseline weight (ie, Grade 1 weight loss). These subjects will restart the study drug(s) at a lower dose once their weight remains stable for at least 1 week and they reached the normal BMI (if the weight loss occurred but it is still above normal BMI, they can restart the study treatment at a lower dose once the weight has been stable for at least 1 week). Normal BMI should be used as the new baseline for further dose reductions. Obesity is defined as body mass index (BMI) percentiles corresponding to 30 kg/m^2, related to the age of the children ([Cole, et al., 2000](#)) or BMI  $\geq$  the 95th percentile for children and teens of the same age and sex ([Ogden, et al., 2002](#)) ([Appendix 7](#) and [Appendix 8](#)).
- e: For asymptomatic laboratory abnormalities, such as Grade  $\geq 3$  elevations of amylase and lipase that are not considered clinically relevant by the investigator, continuation of treatment should be discussed with the Sponsor.
- f: Excluding laboratory abnormalities judged to be non-life-threatening, in which case manage as Grade 3.

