**Control Arm (Arm B): Ifosfamide + Etoposide**

Ifosfamide 3000 mg/m^2/day, IV, daily for 3 consecutive days (Day 1 to 3), every 21 days, for a maximum of 5 cycles.

Etoposide 100 mg/m^2/day, IV, daily for 3 consecutive days (Day 1 to 3), every 21 days, for a maximum of 5 cycles.

Before dose administration on Day 1 of each cycle and prior to a change in dose due to dose reduction, the amount of lenvatinib needed for each subject must be calculated as follows:

$$\text{Scheduled dose (mg/m}^2\text{)} \times \text{body surface area (BSA) (m}^2\text{)} = \text{lenvatinib dose (mg)}$$

Body surface area (BSA) will be calculated using the method that is accepted and customarily used by the clinical site. BSA must be calculated on Day 1 of each cycle based on the subject's current height and body weight. BSA will be used to determine the amount of lenvatinib for each subject. BSA should not be corrected for amputation. The dose should be rounded to the nearest whole number. After adjustment for BSA, the daily dose of lenvatinib should not exceed 24 mg daily.

Subjects will receive study treatment as continuous 21-day cycles in both treatment arms. Treatment cycles will be counted continuously regardless of dose interruptions. If chemotherapy administration is precluded on Day 1 of a treatment cycle, the subject may resume treatment once recovered at the discretion of investigator. Subsequent chemotherapy will be administered every 21 ( $\pm 1$ ) days starting from the timepoint it was resumed.

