#### 9.4.1.1 Lenvatinib Dose Reduction and Interruption Instructions

Adverse events will be graded using CTCAE version 5.0.

Dose reduction and interruptions for subjects who experience lenvatinib related toxicity will be managed as described in [Table 1](#).

The starting dose of lenvatinib is 14 mg/m^2. Dose reductions occur in succession based on the previous dose level. Each dose level reduction is a 20% reduction from the previous dose.

Once the study drug dose level has been reduced, it may not be increased at a later date, unless the dose was mistakenly decreased; in this situation, the sponsor's approval is required to increase the dose.

Refer to the subsections below for management of hypertension, posterior reversible encephalopathy syndrome/reversible posterior leukoencephalopathy syndrome (PRES/RPLS), proteinuria, hepatotoxicity, thromboembolic events, hypocalcemia, gastrointestinal symptoms and acute abdominal pain, and hemorrhage, as appropriate, before consulting the dose modification table below.

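### For subjects held at the 24 mg lenvatinib cap, the BSA formula in Section 9.4.1 conflicts with the 20% reduction rule in Section 9.4.1.1, and from about 2.10 m² it gives no first reduction at all

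*Protocol*

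**What the plan says.** Section 9.4.1 (the general dosing text printed after the Arm B regimen) fixes when the dose is worked out: "Before dose administration on Day 1 of each cycle and prior to a change in dose due to dose reduction". It also fixes how, and makes this mandatory: the mg dose is the product of scheduled dose in mg/m² and BSA. Two limits apply: "The dose should be rounded to the nearest whole number" and "After adjustment for BSA, the daily dose of lenvatinib should not exceed 24 mg daily".

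Section 9.4.1.1 sets the reductions. "The starting dose of lenvatinib is 14 mg/m"² and "Each dose level reduction is a 20% reduction from the previous dose". It adds: "Once the study drug dose level has been reduced, it may not be increased at a later date, unless the dose was mistakenly decreased".

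Table 1 lists the levels as 11.2, 9.0 and 7.2 mg/m². For the first step it offers an alternative, "or 20% reduction of the starting dose) orally QD (one-level reduction"; for the second and third steps the alternative is 20% off the previous dose.

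Section 9.4.1.1.2 requires a restart at a lower dose, one level or 20% down, when BP at or above the 99th percentile (160 mm Hg systolic or 100 mm Hg diastolic) persists despite maximal antihypertensive therapy. Table 1 footnote d also requires a lower dose when obese subjects restart after weight loss.

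**The concern.** The mg/m² level and the 20% cut are presented as the same instruction. They are the same only if the mg dose is proportional to BSA. Once the 24 mg cap binds, the subject is already below 14 mg/m², so moving to 11.2 mg/m² takes away less than 20% of what the subject was receiving and, at a large enough BSA, nothing.

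Two sites following the text could therefore restart identical subjects on different doses after the same intolerable Grade 2 or Grade 3 toxicity. One that follows the formula could return a large subject to the dose that caused the toxicity. Reductions are not rare: in the Study 207 combination cohort (Section 7.3.1), 15 subjects (48.4%) had adverse events leading to dose reduction, although that figure does not separate lenvatinib from chemotherapy.

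**Working it through.** **Inputs.** Starting level 14 mg/m² and 20% steps (Section 9.4.1.1); levels 11.2, 9.0 and 7.2 mg/m² (Table 1); rounding to a whole number, 24 mg cap, and recalculation before a reduction and on each Day 1 (Section 9.4.1).

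**The protocol's own ladder.** 14 × 0.8 = 11.2; × 0.8 = 8.96; × 0.8 = 7.168. These round to 11.2, 9.0 and 7.2, so Table 1 reproduces. No stated number is wrong; the problem is how the ladder meets the cap.

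**Where the cap binds.** 24/14 = 1.714 m².

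**20% rule from 24 mg.** 24 × 0.8 = 19.2; 15.36; 12.29, giving 19, 15 and 12 mg at any BSA.

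**Formula, first step: min(24, round(11.2 × BSA)).** The band edges are 19.5/11.2 = 1.741, 20.5/11.2 = 1.830, 21.5/11.2 = 1.920, 22.5/11.2 = 2.009 and 23.5/11.2 = 2.098 m².

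| BSA (m²) | Formula dose (mg) | Cut from 24 mg | Excess over 19 mg |
|---|---|---|---|
| 1.741 to <1.830 | 20 | 16.7% | 1 |
| 1.830 to <1.920 | 21 | 12.5% | 2 |
| 1.920 to <2.009 | 22 | 8.3% | 3 |
| 2.009 to <2.098 | 23 | 4.2% | 4 |
| from 2.098 | 24 | 0% | 5 |

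Without rounding, the first cut disappears at 24/11.2 = 2.143 m².

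**All three steps by formula**, against 19, 15, 12 by the 20% rule:

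- BSA 1.9: 21.28, 17.1, 13.68, so 21, 17, 14 mg
- BSA 2.0: 22.4, 18.0, 14.4, so 22, 18, 14 mg
- BSA 2.1: 23.52, 18.9, 15.12, so 24, 19, 15 mg

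**Is this just rounding?** For uncapped subjects, round(11.2 × BSA) was compared with round(0.8 × round(14 × BSA)) for BSA 0.500 to 1.714 in steps of 0.001. The two differ at 243 of 1,215 points (20%), never by more than 1 mg, and in both directions (formula higher at 135, lower at 108). A 1 mg gap is therefore ordinary rounding, and the band from 1.741 to 1.830 m² is not counted as a cap effect. From 1.830 m² the gap is 2 mg or more, always upward, and grows with BSA.

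**The next Day 1.** Suppose a site does cut a capped subject with BSA 2.0 to 19 mg. The recalculation at level 11.2 then returns round(22.4) = 22 mg. The no-increase sentence protects the dose level, which is still 11.2 mg/m², so it does not clearly prevent the rise in mg.

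**The case against.** The strongest reply is that the specific section should override the general one. Section 9.4.1.1 and Table 1 govern reductions, and Section 9.4.1.1.2 repeats the 20%. In uncapped subjects the bracketed alternative in Table 1 adds almost nothing, so it may well have been meant for capped ones. A site would also have to enter a one-level reduction that reduces nothing before restarting at 24 mg, so a restart at 21 to 23 mg is the likelier error. This reading is plausible and Table 1 favours it. It does not settle the matter: Section 9.4.1.1 defines the starting dose as 14 mg/m², not as the mg given; Section 9.4.1 expressly applies the formula to reductions; and the favoured reading leaves the later Day 1 recalculation open.

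The harm is also bounded, and that stands. Table 1 requires interruption until recovery first, sponsor approval to resume after more than 28 days off treatment, and discontinuation for Grade 4 (apart from laboratory abnormalities judged non-life-threatening). The formula never exceeds the level's mg/m² except by rounding (24/2.10 = 11.4 against 11.2), and later steps do fall. Footnote d is weaker support than the hypertension text, because BSA is recalculated lower after weight loss.

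Finally, a 20% cut from 24 mg takes large subjects below the listed mg/m² levels: at 2.1 m², 19/2.1 = 9.0 and 12/2.1 = 5.7 mg/m². That is true and the sponsor should know it. It follows from the 20% rule as the protocol states it, not from a new clinical choice.

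**Conclusion.** The inconsistency is real. Two operative rules give different doses for a subject at the cap: beyond rounding from about 1.83 m², and with no first reduction from about 2.10 m², where the 20% rule gives 19 mg. These thresholds rest on rounding to whole mg and on a subject actually receiving 24 mg. The protocol gives no BSA distribution, so the number affected is unknown and may be small. The consequence is confined to dosing safety in Arm A and in Arm B subjects who cross over; sample size, alpha and the primary analysis are unaffected. It should be fixed because the correction is simple and the ambiguity arises when a subject is restarting after toxicity.

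**What to change.** State in Section 9.4.1 and Table 1 that the daily cap falls with the dose level: 24, 19, 15 and 12 mg for 14, 11.2, 9.0 and 7.2 mg/m². The dose at each reduction, and at each later Day 1, is the lesser of rounded level × BSA and that level's cap.

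At all 1,215 uncapped BSA points and all four levels, rounded level × BSA never exceeds these caps, so no uncapped dose changes. At BSA 1.75, 1.8, 1.9, 2.0, 2.1 and 2.2 the rule gives 24, 19, 15, 12 mg throughout, and it stops a Day 1 recalculation from raising a reduced dose above its level's cap.

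The cost is one clarifying sentence in each place and a memo to sites. The design does not change.

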#### 9.4.1.1.1 BLOOD PRESSURE

For children, blood pressure varies by the sex and age of the child and it is closely related to height and weight. Blood pressure will be assessed in terms of percentile for sex, age and height/length. Guidelines to sex, age, and height-specific percentiles of blood pressure are provided in [Appendix 5](#) and [Appendix 6](#). BP that is consistently above the 95th percentile based on sex, age, and height/length for subjects  $<18$  years old; or BP  $\geq 140/90$  mmHg for

subjects  $\geq 18$  to 25 years old requires further evaluation. A referral to a cardiologist is recommended for patients who develop hypertension during the study. Ideally, cardiovascular assessments and the management of hypertension should be supervised by a cardiologist. Exercise, excitement, coughing, crying, and struggling may raise the systolic pressure of children as much as 40 to 50 mmHg greater than their usual level. Variability in blood pressure in children of approximately the same age and body build should be expected and serial measurements should always be obtained when evaluating a patient with hypertension. BP values for the management of hypertension for participants 18 to 25 years old are included in parentheses in [Section 9.4.1.1.1](#).

#### 9.4.1.1.2 MANAGEMENT OF HYPERTENSION

Hypertension is a recognized side-effect of treatment with drugs inhibiting VEGF signaling. Investigators should therefore ensure that subjects enrolled to receive treatment with lenvatinib have BP  $< 95$ th percentile [BP  $\leq 150/90$  mm Hg] for sex, age, and height/length at the time of study entry and, if known to be hypertensive, have been on a stable dose of antihypertensive therapy for at least 1 week before Cycle 1 Day 1. Early detection and effective management of hypertension are important to minimize the need for lenvatinib dose interruptions and reductions.

Regular assessment of BP should be conducted as detailed in the Schedule of Procedures/Assessments ([Table 5](#) and [Table 6](#)). Hypertension will be graded using CTCAE v5.0, based on BP measurements only (and not on the number of antihypertensive medications).

If the subject's initial BP measurement is elevated (systolic BP  $\geq 95$ th percentile [BP  $\geq 140$  mm Hg] or diastolic BP  $\geq 95$ th percentile [BP  $\geq 90$  mm Hg]), the BP measurement should be repeated at least 5 minutes later. The mean value of 2 measurements at least 5 minutes apart is defined as 1 BP assessment. If the BP assessment (ie, the mean of the 2 BP measurements obtained at least 5 minutes apart) is elevated (systolic BP  $\geq 140$  mm Hg or diastolic BP  $\geq 90$  mm Hg), a confirmatory assessment should be obtained at least 30 minutes later by performing 2 measurements (at least 5 minutes apart) to yield a mean value.

Antihypertensive agents should be started as soon as elevated BP (systolic BP  $\geq 95$ th percentile [BP  $\geq 140$  mm Hg] or diastolic BP  $\geq 95$ th percentile [BP  $\geq 90$  mm Hg]) is confirmed on 2 assessments obtained 30 minutes apart. The choice of antihypertensive treatment should be individualized to the subject's clinical circumstances and follow standard medical practice. For previously normotensive subjects, monotherapy with one of the classes of antihypertensives should be started when systolic BP  $\geq 95$ th percentile [BP  $\geq 140$  mm Hg] or diastolic BP  $\geq 95$ th percentile [BP  $\geq 90$  mm Hg] is first observed on 2 assessments obtained 30 minutes apart. For those subjects already on antihypertensive medication, treatment modification may be necessary if hypertension persists.

Lenvatinib should be withheld in any instances where a subject is at imminent risk to develop a hypertensive crisis or has significant risk factors for severe complications of uncontrolled

hypertension (eg, BP  $\geq$ 99th percentile [BP  $\geq$ 160/100 mm Hg], significant risk factors for cardiac disease, intracerebral hemorrhage, or other significant comorbidities). Once the subject has been on the same antihypertensive medications for at least 48 hours and the BP is controlled, lenvatinib should be resumed as described below.

During the Treatment Period, subjects with systolic BP  $\geq$ 99th percentile (BP  $\geq$ 160 mm Hg) or diastolic BP  $\geq$ 99th percentile (BP  $\geq$ 100 mm Hg) must have their BP monitored on Day 15 (or more frequently as clinically indicated) until systolic BP has been  $<$ 95th percentile ( $\leq$ 150 mm Hg) and diastolic BP has been  $<$ 95th percentile ( $\leq$ 95 mm Hg) for 2 consecutive treatment cycles. If a repeat event of systolic BP  $\geq$ 99th percentile (BP  $\geq$ 160 mm Hg) or diastolic BP  $\geq$ 99th percentile (BP  $\geq$ 100 mm Hg) occurs, the subject must resume the Day 15 evaluation until systolic BP has been  $<$ 95th percentile ( $\leq$ 150 mm Hg) and diastolic BP has been  $<$ 95th percentile ( $\leq$ 95 mm Hg) for 2 consecutive treatment cycles.

The following guidelines should be followed for the management of systolic BP  $\geq$ 99th percentile (BP  $\geq$ 160 mm Hg) or diastolic BP  $\geq$ 99th percentile (BP  $\geq$ 100 mm Hg) confirmed on repeat measurements after at least 30 minutes:

- Continue lenvatinib and institute antihypertensive therapy for subjects not already receiving this.
- For those subjects already on antihypertensive medication, the dose of the current agent may be increased, if appropriate, or 1 or more agents of a different class of antihypertensive should be added.
- If systolic BP  $\geq$ 99th percentile (BP  $\geq$ 160 mm Hg) or diastolic BP  $\geq$ 99th percentile (BP  $\geq$ 100 mm Hg) persists despite maximal antihypertensive therapy, then lenvatinib administration should be interrupted and restarted at a lower dose QD (one dose level reduction [20%]) only when systolic BP  $<$ 95th percentile (BP  $\leq$ 150 mm Hg) and diastolic BP  $<$ 95th percentile (BP  $\leq$ 95 mm Hg) and the subject has been on a stable dose of antihypertensive medication for at least 48 hours.
  - If systolic BP  $\geq$ 99th percentile (BP  $\geq$ 160 mm Hg) or diastolic BP  $\geq$ 99th percentile (BP  $\geq$ 100 mm Hg) recurs on the first dose reduction despite optimal management of hypertension with antihypertensive medications (either by dose increase or the addition of a different class of antihypertensive), then lenvatinib administration should be interrupted and restarted at an additional dose reduction only when systolic BP  $<$ 95th percentile (BP  $\leq$ 150 mm Hg) and diastolic BP  $<$ 95th percentile (BP  $\leq$ 95 mm Hg) and the subject has been on a stable dose of antihypertensive medication for at least 48 hours.
  - If systolic BP  $\geq$ 99th percentile (BP  $\geq$ 160 mm Hg) or diastolic BP  $\geq$ 99th percentile (BP  $\geq$ 100 mm Hg) recurs on the second dose reduction despite optimal management of hypertension with antihypertensive medications (either by dose increase or the addition of a different class of antihypertensive), then lenvatinib administration should be interrupted and restarted at a third dose reduction only when systolic BP  $<$ 95th percentile (BP  $\leq$ 150 mm Hg and diastolic BP  $<$ 95th

[figure not shown]
percentile (BP  $\leq$ 95 mm Hg) and the participant has been on a stable dose of antihypertensive medication for at least 48 hours.

- Additional dose reduction should be discussed with the Sponsor.

The following guidelines should be followed for the management of Grade 4 hypertension (life-threatening consequences):

- Institute appropriate medical management
- Discontinue lenvatinib

Figure 2 shows the procedures associated with the management of hypertension.

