#### 9.5.1.4.4 VITAL SIGNS AND WEIGHT MEASUREMENTS

Vital sign measurements (ie, systolic and diastolic blood pressure [BP] [mmHg], pulse [beats per minute], respiratory rate [per minute]), body temperature (in centigrade), weight (kg), and height (cm) will be obtained at the visits designated in the Schedule of Assessments ([Table 5](#) and [Table 6](#)) by a validated method. Blood pressure and pulse will be measured after the subject has been resting for 5 minutes. All BP measurements should be performed on the same arm, preferably by the same person. On Cycle 1 Day 8, subjects will have a telephone or clinic visit to assess for the development of early toxicity. Subjects will be provided with a BP cuff to monitor BP at home or can have the measurement done by a local healthcare provider, and will report the C1D8 measurement at telephone contact. An unscheduled visit can occur prior to C1D15 if deemed necessary by the investigator.

Only 1 BP measurement is needed for subjects with systolic BP  $<$ 95th percentile (BP  $<$ 140 mm Hg) and diastolic BP  $<$ 95th percentile (BP  $<$ 90 mmHg). If the subject's initial BP measurement is elevated (systolic BP  $\geq$ 95th percentile [ $\geq$ 140 mmHg] or diastolic BP  $\geq$ 95th percentile [ $\geq$ 90 mmHg]), the BP measurement should be repeated at least 5 minutes later. The mean value of 2 measurements at least 5 minutes apart is defined as 1 BP assessment. If the BP assessment (ie, the mean of the 2 BP measurements obtained at least 5 minutes apart) is elevated (systolic BP  $\geq$ 95th percentile [ $\geq$ 140 mm Hg] or diastolic BP  $\geq$ 95th percentile [ $\geq$ 90 mm Hg]), a confirmatory assessment should be obtained at least 30 minutes later by performing 2 measurements (at least 5 minutes apart) to yield a mean value.

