#### 9.7.1.8.4 VITAL SIGNS

Descriptive statistics for vital signs parameters (ie, systolic and diastolic BP, pulse, respiratory rate, temperature, weight, and height) and changes from baseline will be presented by visit and treatment group.

Percentiles for BP values (only for subjects <18 years old) will also be summarized using a shift table of worst postbaseline from Baseline measurement by categories (<90th percentile, 90th to 95th percentile, 95th to  $\leq$ 99th percentile, systolic BP or diastolic BP >99th percentile). See [Appendix 5](#) and [Appendix 6](#) for detail on percentiles.

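### Section 9.4.1.1.2 orders the confirmatory blood pressure assessment at 140/90 mm Hg only, whereas the linked steps and Section 9.5.1.4.4 use the 95th percentile for subjects under 18

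*Protocol*

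**What the plan says.** Section 9.4.1.1.2 of the Protocol (Amendment 02) sets out three linked steps.

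1. First reading: "If the subject's initial BP measurement is elevated (systolic BP $\geq 95$ th percentile [BP $\geq 140$ mm Hg", with 90 mm Hg as the bracketed diastolic value. The reading is then repeated at least 5 minutes later, and the mean of the two counts as one assessment.
2. Confirmation: if that mean "is elevated (systolic BP $\geq 140$ mm Hg or diastolic BP $\geq 90$ mm Hg), a confirmatory assessment should be obtained". The second assessment follows at least 30 minutes later.
3. Treatment: "Antihypertensive agents should be started as soon as elevated BP (systolic BP $\geq 95$ th percentile [BP $\geq 140$ mm Hg", again with 90 mm Hg for diastolic, once this "is confirmed on 2 assessments obtained 30 minutes apart".

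Section 9.5.1.4.4 describes step 2 again, but its condition is the 95th percentile with the adult values in brackets. It ends "mm Hg]), a confirmatory assessment should be obtained at least 30 minutes later".

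Section 9.4.1.1.1 says that children are assessed by percentile for sex, age and height. It explains the notation: "BP values for the management of hypertension for participants 18 to 25 years old are included in parentheses". For those values it points to Section 9.4.1.1.1, which is itself; they are in Section 9.4.1.1.2.

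**The concern.** Two sections give different triggers for the same action in subjects under 18. Step 2 controls treatment: step 3 needs two assessments 30 minutes apart, and within Section 9.4.1.1.2 only step 2 orders the second one. If step 2 is applied at 140/90, a child whose mean lies between the 95th percentile and 140/90 is not sent for confirmation and cannot meet the condition for starting antihypertensives.

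Hypertension is a known effect of VEGF inhibition. The section itself says that early detection and effective management matter for limiting lenvatinib interruptions and reductions. The trial enrols from age 2 and must randomize at least 36 of about 72 subjects under 17. The blood pressure footnotes of all three schedules (Table 5 footnote h, Table 6 footnote e, Table 7 footnote e) send sites to Section 9.4.1.1.2 for management, not to Section 9.5.1.4.4.

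**Working it through.** The protocol gives no figure to reproduce here. The check compares the thresholds and then measures the gap from the protocol's own tables.

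**Thresholds side by side**

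| Step | Section | Under 18 | 18 to 25 |
|---|---|---|---|
| First reading elevated | 9.4.1.1.2 | 95th percentile | 140/90 |
| Mean elevated, order confirmation | 9.4.1.1.2 | none stated | 140/90 |
| Mean elevated, order confirmation | 9.5.1.4.4 | 95th percentile | 140/90 |
| Start antihypertensives | 9.4.1.1.2 | 95th percentile | 140/90 |

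Step 2 of Section 9.4.1.1.2 can be read in two ways. If its parenthesis holds the adult values, as Section 9.4.1.1.1 says of values in parentheses, the step has no criterion for subjects under 18. If it applies to everyone, it conflicts with Sections 9.4.1.1.1 and 9.5.1.4.4. Neither reading is right for children.

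**Inputs.** The 95th and 99th percentile rows of Appendix 5 (boys) and Appendix 6 (girls), ages 2 to 17, seven height columns: 2 sexes × 16 ages × 7 heights = 224 cells. Of these, 2 × 12 × 7 = 168 are at ages 2 to 13 and 2 × 4 × 7 = 56 at ages 14 to 17.

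**Does the gap exist?** Gap = 140 − 95th percentile (systolic) and 90 − 95th percentile (diastolic).

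- Systolic 95th percentile below 140: 223 of 224. The exception is boys of 17 in the tallest column, where it equals 140.
- Diastolic 95th percentile below 90: 224 of 224 (maximum 89).

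**How wide is it?** Median (range), mm Hg:

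| Ages | Systolic gap | Diastolic gap |
|---|---|---|
| 2–13 | 25 (10–39) | 14 (7–31) |
| 14–17 | 10.5 (0–17) | 6 (1–10) |

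**Does it reach past the 99th percentile?**

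- Systolic 140 exceeds the 99th percentile in 210 of 224 cells: all 112 for girls, all 84 for boys aged 2 to 13, and 14 of 28 for boys aged 14 to 17 (112 + 84 + 14 = 210).
- Both 140 and 90 exceed the 99th percentile in 156 of 168 cells at ages 2 to 13 and in 10 of 56 at ages 14 to 17 (156 + 10 = 166 of 224). In adolescents the gap therefore lies mainly between the 95th and 99th percentiles.

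**Two worked cases, both at median height**

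- Boy of 15: 95th percentile 131/83, 99th 138/91. Gap: 140 − 131 = 9 systolic, 90 − 83 = 7 diastolic. A mean of 135/86 is above his 95th, below his 99th and below 140/90. Section 9.5.1.4.4 orders confirmation; Section 9.4.1.1.2 does not.
- Boy of 10: 95th percentile 119/80, 99th 127/88. Gap: 140 − 119 = 21 systolic, 90 − 80 = 10 diastolic. A mean of 130/85 is above his 99th systolic value yet does not meet step 2.

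**Does the 99th-percentile rule close the gap?** Only in part. Later text in Section 9.4.1.1.2 sets Day 15 monitoring and management at the 99th percentile, but the management guidelines apply to values "confirmed on repeat measurements after at least 30 minutes". They presuppose the repeat without ordering it. The 15-year-old above falls outside that rule altogether.

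**The case against.** The strongest reply is that this is a dropped phrase rather than two opposed instructions. Step 2 does not say to omit confirmation below 140/90, so a site that follows Section 9.5.1.4.4 breaches nothing. The steps on either side use the 95th percentile, and an investigator reaches step 2 for a child only because the first reading was at or above it. Section 9.4.1.1.1 sets the percentile scale, calls for further evaluation of under-18 readings consistently above the 95th percentile, and advises serial measurements. The schedule footnotes repeat the under-18 rule. Figure 2, which shows the procedure for managing hypertension, is not in the text available here and may be right. The cell counts describe reference tables, not patients, and the widest gaps are at ages below the 15 to 19 peak in incidence that the protocol cites.

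Much of this stands. The intended threshold is clear, many investigators will apply it, and the frequency of any delay is unknown. It does not dispose of the point. None of the cited text outside Section 9.5.1.4.4 orders the 30-minute confirmation for a child, and the schedule footnotes send sites to the section with the defective sentence. That the intended meaning can be inferred does not justify leaving the wrong number at a decision point in a paediatric safety rule.

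**Conclusion.** The concern holds. Step 2 of Section 9.4.1.1.2 is wrong as written for subjects under 18 and disagrees with the identical step in Section 9.5.1.4.4. A gap below 140/90 exists on at least one component in every age, sex and height cell of Appendices 5 and 6 for ages 2 to 17. The consequence is a possible delay in confirmation and in antihypertensive treatment at a site that follows Section 9.4.1.1.2 literally. The number of subjects affected cannot be derived from the document.

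The conclusion rests on the text alone; Figure 2 could soften it if it shows the percentile trigger. Adverse event recording, CTCAE grading from blood pressure measurements, the statistical design, and the planned shift table ("Percentiles for BP values (only for subjects <18 years old) will also be summarized") are not affected. The self-referring pointer in Section 9.4.1.1.1 is a clerical slip and carries no weight of its own. This should be corrected, but it does not threaten the trial's conclusions.

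**What to change.** In Section 9.4.1.1.2, change the condition for the confirmatory assessment to systolic at or above the 95th percentile [140 mm Hg or more] or diastolic at or above the 95th percentile [90 mm Hg or more], as in Section 9.5.1.4.4. Redirect the pointer at the end of Section 9.4.1.1.1 to Section 9.4.1.1.2. Check that Figure 2 shows the same trigger, and correct it if not.

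The cost is one sentence and one cross-reference in the next amendment, with a clarification note to sites in the meantime. No visit is added, because Section 9.5.1.4.4 already requires this confirmation.

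### Blood pressure at or above the 99th percentile (160/100 mm Hg) appears both as a reason to withhold lenvatinib and as a state in which to continue it.

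*Protocol*

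**What the plan says.** Both instructions are in Protocol Section 9.4.1.1.2 (Management of Hypertension), in the current Amendment 02 text.

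- **Withhold paragraph.** "Lenvatinib should be withheld in any instances where a subject is at imminent risk to develop a hypertensive crisis". A second trigger in the same sentence is the presence of marked risk factors for serious harm should hypertension stay uncontrolled. The examples that follow are BP at or above the 99th percentile (160/100 mm Hg), cardiac risk factors, intracerebral hemorrhage and other significant comorbidities. Resumption is tied to at least 48 hours on the same antihypertensives: "and the BP is controlled, lenvatinib should be resumed as described below".
- **Bulleted guideline, two paragraphs later.** "The following guidelines should be followed for the management of systolic BP" at or above the 99th percentile (160 mm Hg), or diastolic BP at or above the 99th percentile (100 mm Hg), "confirmed on repeat measurements after at least 30 minutes". The first bullet reads: "Continue lenvatinib and institute antihypertensive therapy for subjects not already receiving this". The second deals with stepping up treatment in subjects already on antihypertensives. The third brings in interruption, with restart one dose level lower, when BP at this level persists despite maximal antihypertensive therapy.

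Table 1 footnote b (Section 9.4.1.1) also places medical management of hypertension before any interruption or dose reduction.

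**The concern.** A site facing a first confirmed reading at this level can follow the protocol and either stop the drug or carry on with it. Section 9.4.1.1.2 itself describes hypertension as a recognised effect of drugs that inhibit VEGF signalling, and the subjects are 2 to 25 years old, so the ambiguity concerns safety.

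It can also reach the data. Section 9.7.1.8.1 plans summaries of dose intensity, dose reductions and treatment interruptions. With about 80 sites (Section 6), part of what is seen in Arm A could reflect how each site read the section. Arm B subjects who cross over are sent to the same section by Table 7 footnote e.

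**Working it through.** No figure in the plan depends on this point, so the check is a comparison of the two rules.

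| Element | Withhold paragraph | Bulleted guideline |
|---|---|---|
| BP, as a percentile | at or above the 99th | systolic or diastolic at or above the 99th |
| BP, in mm Hg (ages 18 to 25, Section 9.4.1.1.1) | at or above 160/100 | systolic at or above 160, or diastolic at or above 100 |
| Confirmation | none stated | repeat after at least 30 minutes |
| Other risk factor needed | no: BP is a separate example | no |
| First action | withhold | continue, start antihypertensives |
| Interruption | at once | when the level persists despite maximal therapy |
| Precedence over the other rule | not stated | not stated |

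**Test case.** Take a 20-year-old on no antihypertensives with a first confirmed reading of 165/105 mm Hg.

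1. Withhold rule: 165 is at least 160 and 105 is at least 100, so the example is met whether the slash means both values or either one. Action: withhold.
2. Bulleted guideline: systolic is at least 160 and the reading is confirmed. Action: continue and start treatment.
3. Both rules apply and the actions differ.

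**Does confirmation separate the rules?** No. The withhold rule has no confirmation condition, so it covers confirmed readings as well. If confirmation were the divider, an unconfirmed reading would draw the stricter action.

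**Do other risk factors separate them?** The text does not say so. BP at this level is one item in a list of examples, not tied to the comorbidities after it.

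**Resumption.** The withhold paragraph refers forward for the restart. The only restart rules that follow are at a reduced dose, after BP has persisted or recurred despite treatment. The dose level after a first withholding is therefore not stated. This matters because Section 9.4.1.1 does not allow a reduced dose to be raised later unless the reduction was a mistake and the sponsor approves. Each level is a 20% reduction. A site that takes the forward reference to mean the reduced-dose rule would fix that reduction in place, while another site would not have interrupted at all.

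**Scale.** Section 7.3.1 reports hypertension in 36% of subjects on single-agent lenvatinib in Study 207. Arm A has 36 subjects: 0.36 × 36 = 12.96, about 13. That is any-grade hypertension on the single agent. The protocol gives no rate at the 99th percentile or 160/100 mm Hg, so the number who would meet both rules cannot be derived.

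**The case against.** The best counter-argument is that the withhold paragraph is a general safety override. Its test is a judgement about imminent crisis or severe complications, the BP value only illustrates that judgement, and the bullets are the stepwise procedure for an ordinary confirmed reading. The reference to uncontrolled hypertension would then fit the bullet on persistence despite maximal therapy. This may be what was meant, but the wording does not limit the example in that way.

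Other points narrow the problem:

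- The bullets do not expressly forbid earlier withholding. That interruption waits for failure of maximal therapy is the natural reading of their sequence, not an explicit prohibition.
- The clearest conflict is in a subject not yet on antihypertensives. Section 9.4.1.1.2 starts treatment at a confirmed 95th percentile (140 or 90 mm Hg), so some subjects will already be treated. Still, the bullet's qualifier about subjects not already receiving treatment most naturally limits the antihypertensive clause, not the instruction to continue lenvatinib.
- Table 1 footnote b and the recommended cardiologist referral (Section 9.4.1.1.1) lean towards medical management first. Neither amends the withhold sentence.
- Figure 2 is not visible in the text available and may set out an order of steps. It could guide sites in practice, but it would not remove the conflict in the prose.
- The figure of 13 does not size the problem, and any effect on dose intensity is a possibility that has not been quantified.

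**Conclusion.** The contradiction is real. At the same blood pressure, one paragraph says withhold and another says continue, with no stated order of precedence. A reading of 165/105 mm Hg satisfies both on any interpretation of the slash. The restart dose after a first withholding is a linked gap.

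The consequence is inconsistent safety conduct, and possibly site-dependent interruptions and dose intensity in Arm A. The number affected is unknown; about 13 subjects is any-grade, single-agent context only. No sample size, event count, power or alpha figure is touched. The conclusion rests on the prose of Section 9.4.1.1.2 alone and takes no position on which action is clinically right. It should be corrected, but it does not threaten the primary analysis.

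**What to change.** Reconcile the two paragraphs of Section 9.4.1.1.2 so that a first confirmed BP at or above the 99th percentile or 160/100 mm Hg leads to one stated action. Name the criterion that separates subjects in whom lenvatinib is withheld from the rest, and say which rule prevails if both could apply. State explicitly which restart rule the forward reference means after a first withholding. Check Figure 2 and Table 1 footnote b for agreement. The clinical content of each of these is for the sponsor's clinical team to decide.

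The cost is clarifying wording and a memo to sites. No change to the sample size or the analysis is needed.
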